7.2 Multiple Ascending Dose (MAD) Cohort

7.2.1 Sample Size. The study sample size will be 24 for the MAD arm of the protocol in cohorts of 8. Participants will be randomized to treatment or placebo in a 3:1 ratio. The first 2 subjects of each cohort will be sentinels (1 treatment, 1 placebo). Continuation of the study in each cohort will occur if no clinical or biochemical adverse effects are observed in the sentinels as determined by the Safety Review Committee (SRC). Escalation to the higher dose will occur if no clinical or biochemical adverse effects are observed after a 10 day follow-up period as determined by the SRC.

7.2.2 LSALT Peptide Dosing. The doses for the MAD cohorts will be determined by the SRC based on the results from the prior SAD and MAD arms of the study. These doses have been determined to be 1 mg, 2.5 mg and 5 mg. LSALT peptide will administered intravenously once daily for 3 days. The starting dose for the Phase 1 clinical study will be subject to change and reassessed based on the results from the SAD cohort and in accordance with FDAs guidance document for estimating a safe starting dose in initial clinical trials.

7.2.3 Confinement. Participants will be confined for days -1 to day 4 during the administration of the LASLT peptide.

7.2.4 Replacement. In the event of participant drop-out, participants from the reserve pool will be enrolled in the study and randomized.

7.2.5 MAD Study Procedures

- **Day -29. Pretreatment Evaluation and Randomization.** 29 days prior to study initiation, enrolled participants will undergo informed consent, followed by a complete history and physical examination (including body weight and height) vital signs (seated), alcohol breath test, drugs of abuse test, baseline fasting laboratory studies (CBC, clinical chemistry) including coagulation profile (INR and PTT), urinalysis, 12-lead, electrocardiogram (supine) and chest x-ray (single PA view). Women of child-bearing age will have a β -hCG to rule out pregnancy. Participants will then be randomized.
- **Day -1.** Admission to unit. Participants will undergo a clinical evaluation including complete vital signs and physical examination, 12-lead electrocardiogram (supine), drugs of abuse and alcohol breath test, urinalyses, 25 ml of blood drawn for safety laboratory investigations including CBC, clinical chemistries, urinalysis and women of child-bearing age will have a urine pregnancy test to rule out pregnancy.
- **Day 1.** Participants will undergo clinical evaluation including vital signs. 5 ml of blood will be drawn at 30 minutes prior to LSALT peptide infusion for baseline PK measurements. LSALT peptide infusion will begin and run over 2 hours. 5 ml of blood will be drawn at 15, 30, 45 60, 75, 90, 105, 120, 125, 130, 135, 140 minutes, and 3 hours from the onset of the LSALT infusion.

- **Day 2.** Participants will undergo a clinical evaluation, including vital signs, a brief history and symptom directed physical exam. 25 ml of blood will be drawn for laboratory investigations, including CBC, clinical chemistries and coagulation profile (INR and PTT), urinalysis and 24 hour PK sample (from the onset of the first LSALT infusion). An ECG will also be completed. If the participant shows no adverse events, they will receive the second dose of the LSALT peptide.
- **Day 3.** Participants will undergo a clinical evaluation, including vital signs, a brief history and a symptom directed physical exam. If the participant shows no adverse events, they will receive the third dose of the LSALT peptide. 5 ml of blood will be drawn at 15, 30, 45 60, 75, 90, 105, 120, 125, 130, 135, 140 minutes, and 3 hours from the onset of the LSALT infusion.
- **Day 4.** Participants will undergo a clinical evaluation, including vital signs and a symptom directed physical examination. 25 ml of blood will be drawn for laboratory investigations, including CBC, clinical chemistries, coagulation profile (INR and PTT) and a 72 hour PK sample (from the onset of the first LSALT infusion). A urinalysis, CXR and ECG will also be completed. If the participant shows no adverse events, they will be discharged from the unit.
- **Day 7.** Participants will return for a clinical evaluation, including a brief history, vital signs and a symptom directed physical examination. 25 ml of blood will be drawn for laboratory investigations, including CBC, clinical chemistries, coagulation profile (INR and PTT) and a 96 hour PK sample (from the end of the 3rd LSALT infusion). A urinalysis will also be completed.
- **Day 14.** Participants will return for a clinical evaluation, including a brief history, vital signs and symptom directed physical examination. 25 ml of blood will be drawn for laboratory investigations, including CBC, clinical chemistries. A urinalysis will also be completed and a sample of blood drawn for anti-drug antibodies.
- **Day 21.** Participants will return for a clinical evaluation, including a brief history, vital signs and a complete physical examination. 25 ml of blood will be drawn for laboratory investigations, including CBC, clinical chemistries. A urinalysis and ECG will also be completed. Women of child-bearing age will also have a urine pregnancy test
- **Day 28.** Begin Cohort 2 or 3. Conducted as per Cohort 1 to day 21.

Treatment and Assessment Timetable (MAD)

Study Day	Screen -29 to -2	-1	1	2	3	4	7	14	21
In patient period		X	X	X	X				
Informed consent	X								
Vital signs	X	X	X ⁶	X ⁶	X ⁶	X	X	X	X
Physical Examination	X	X		X	X	X	X	X	X
Alcohol Breath Test	X	X							
Drugs of Abuse	X	X							
Urinalysis	X	X		X		X	X	X	X
CBC	X	X		X		X	X	X	X
Chemistry	X	X		X		X	X	X	X
Creatinine/eGFR	X	X		X		X	X	X	X
LFTs	X	X		X		X	X	X	X
PK			X ¹	X ²	X ³	X ⁴	X ⁵		
INR/PTT	X			X		X	X		
CXR	X					X			
ECG	X	X	X ⁷	X ⁷	X ⁷	X			X

B-hCG ⁸	X	X							X
Adverse Event	X		X	X	X	X	X	X	X
Anti-Drug Antibodies								X	
LSALT Administration			X	X	X				
Discharge from unit						X			
Follow up							X	X	X

Note: Fasting for blood sampling required for Screening and post dose Follow up. Participants will be required to have fasted from all food and drink except water for at least 8 hours prior to blood sampling.

1. PK blood samples: 5 ml of blood will be drawn at 30 prior to LSALT peptide infusion for baseline PK measurements. LSALT peptide infusion will begin and run over 2 hours. 5 ml of blood will be drawn at 15, 30, 45 60, 75, 90, 105, 120, 125, 130, 135, 140 (+/- 2 min) minutes, 3 hours (+/- 5 min) from the onset of the LSALT infusion
2. PK blood sample: 24 hours (+/- 30 mins) from the onset of the 1st infusion.
3. PK blood samples: 5 ml of blood will be drawn at 30 prior to LSALT peptide infusion. LSALT peptide infusion will begin and run over 2 hours. 5 ml of blood will be drawn at 15, 30, 45 60, 75, 90, 105, 120, 125, 130, 135, 140 (+/- 2 min) minutes and 3 hours (+/- 5 min) from the onset of the LSALT infusion
4. PK blood sample: 72 hours (+/- 30 mins) from the onset of the first LSALT infusion
5. PK blood sample: 96 hours (+/- 30 mins) from the end of the third LSALT infusion
6. Vital signs dosing day (seated): pre dose (+/-30 mins), 1 hour (+/- 10mins) , 2 hour (+/- 10 mins) 6 hours (+/- 15min) and 10 hours post completion of infusion (+/- 30 mins)
7. 12 lead electrocardiogram (supine): pre dose (+/- 30 mins), 2 hours (+/- 15 mins) and 8 hours post completion of infusion (+/- 30 mins)
8. Pregnancy test will be via serum B-hCG at Screening and a urine pregnancy test at pre dose (Study Day -1,) and follow up

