3.5 Drug Metabolism and Pharmacokinetics

Plasma levels of LSALT peptide were measured post-intravenous dosing of 100, 250 and 450 mg/kg in rats. Terminal elimination half-lives of 0.66 – 1.17 hr and MRT_{obs} values of 0.58 – 0.85 hr were observed for LSALT peptide. The AUC_{0- ∞} was linear and close to proportional with dose.

LSALT peptide is stable in human plasma for up to 90 minutes with no detectable metabolic/proteolytic fragments as measured by mass spectrometry. LSALT peptide is undetectable in whole blood in the absence of phosphoric acid due to red or white blood cell binding. In human whole blood, 90% or more of the LSALT peptide is contained within the cellular compartment. LSALT peptide however is compatible with blood and does not induce red blood cell hemolysis. Work is ongoing to identify LSALT peptide volume of distribution, tissue biodistribution, and excretion.

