3.8 Study Rationale

Acute kidney injury is a devastating complication for patients undergoing surgery, diagnostic imaging or in the context of critical illness. Currently there are no effective therapies to prevent or minimize acute kidney injury. Inflammation is an important factor

¹ An allergic reaction is marked by the activation of the immune system by an allergen and includes signs that involve the skin, nose/throat, upper airway, GI tract, lungs and cardiovascular system. While the animals exhibited clinical features that would be seen in an allergic reaction, given its self-limited nature and severity, and the fact that they occurred only during the infusion, the findings are considered to represent a non-immune infusion reaction. Thus, the effects were considered pseudo-allergic or anaphylactoid.

in the pathogenesis of acute kidney injury. Given its favorable initial toxicology profile, the administration of LSALT peptide to target inflammation and prevent acute kidney injury has the potential to provide a significant clinical impact. Since LSALT peptide is a new drug, this phase I study to evaluate safety and pharmacokinetics is the first step needed to advance the LSALT peptide for the prevention of acute kidney injury in humans.

A third MAD cohort of 5 mg administered intravenously daily for 3 days is being proposed to obtain additional pharmacokinetic data.

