7.3.5 Safety Assessment. Patients will be monitored during drug administration and up to 3 weeks thereafter. Patients will be monitored for adverse effects using vital signs (seated, respiratory rate, heart rate, blood pressure, temperature and pulse oximetry), hematology, clinical chemistry, seated, supine single 12-lead electrocardiograms, chest radiography, and urine testing. Adverse events during the study will be reported and graded as per the CTCAE version 5.0.

7.3.6 Laboratory Testing. 25 mL of blood will be drawn for fasting laboratory assessment (hematology and clinical chemistries) at screening, baseline (pre-dose Day 1), and on study days 2, 4, and 7 (refer to Flow Chart). Additional bloodwork will be drawn at day 14 in the MAD cohort. In addition, 5 mL of blood will be collected for pharmacokinetic analysis at 30-minutes pre-dose, then 15, 30, 45, 60, 75, 90, 105, 120, 125, 130, 135, 140 minutes, and 3 hours from the onset of the LSALT infusion, 24 hours post drug administration on day 2 (from onset of 1st LSALT dose, SAD and MAD cohort), 72 hours post drug administration on day 4 (from onset of 1st LSALT dose, SAD and MAD cohort), and 96 hours post drug administration on day 7 (from onset of 3rd LSALT dose, MAD cohort). Participants will be required to have fasted from all food and drink except water for at least 8 hours prior to blood sampling.

Baseline hematology will include hemoglobin, hematocrit, total white blood cell count, white blood cell differentiation and platelet count. INR and PTT will also be performed. Clinical chemistry (fasting state) will include total protein, albumin, sodium, potassium, chloride, bicarbonate, random glucose, insulin, calcium, magnesium, phosphate, urea, uric acid, AST, ALT, ALP, LDH, TBili, GGT, creatinine, triglycerides, total cholesterol, and urinalysis (dipstick for protein, blood, glucose, ketones, pH, leukocytes and microscopic examination only if dipstick is not completely negative). Urinalysis will be conducted at the same times as the blood draws for hematology and clinical chemistries.

7.3.7 Women of Childbearing Potential. Women of childbearing potential (defined as women with regular menses, women with amenorrhea, women with irregular cycles, women using a contraceptive method that precludes withdrawal bleeding,) are required to have a negative serum pregnancy test (β -HCG) during screening and at the end of the study treatment.

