10.1.6 Administration

LSALT peptide is diluted in 100 ml of 0.9% sodium chloride and administered intravenously over 2 hours ± 5 minutes. Based upon evaluation of tolerability and safety of the first cohort, and consistent with the adaptive design, infusion rates could be increased or decreased for subsequent cohorts, as determined by the SRC.

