$\%AUC_{exp}$	Percentage of AUC_{0-inf} due to extrapolation from the time of last concentration to	$(1 - AUC_{0-t}/AUC_{0-inf}) * 100$

This document is confidential.

Parameter	Definition	Method of Determination
	infinity.	
C_{max}	Maximum observed plasma concentration on.	Observed directly from data
T_{max}	Time to reach C_{max} . If the maximum value occurs at more than 1 timepoint, T_{max} is defined as the first timepoint with this value.	Observed directly from data
$t_{1/2}$	Apparent first-order terminal elimination half-life.	$\ln(2)/\lambda_z$
λ_z	Apparent first-order terminal elimination rate constant.	Estimated by linear regression of the terminal elimination phase of the log-linear drug concentration-time curve.
Cl/F	Apparent total body clearance.	Estimated as Dose/ AUC_{0-inf}
V_z/F	Apparent volume of distribution.	Estimated as Dose/ $(\lambda_z \times AUC_{0-inf})$
RAUC	Accumulation Ratio for AUC.	$AUC_{0-12} \text{ or } AUC_{0-24} \text{ Day 3} / AUC_{0-12} \text{ or } AUC_{0-24} \text{ Day 1}$
RC_{max}	Accumulation Ratio for C_{max} .	$C_{max} \text{ Day 3} / C_{max} \text{ Day 1}$

Note: λ_z will be the negative of the estimated slope of the linear regression of the log-transformed concentration (natural logarithm) versus time profile in the terminal elimination phase. At least three concentration points will be used in estimating λ_z . The time point where log-linear λ_z calculation begins (λ_z Lower), and the actual sampling time of the last quantifiable concentration used to estimate the λ_z (λ_z Upper) will be reported with the correlation coefficient from the linear regression to calculate λ_z .

Note: tau is the dosing interval for steady-state data.

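### If the protocol's section 7.2.5 grid governs, MAD sampling stops 1 h after the infusion and resumes at 24 h, which leaves half-life and Vz poorly supported above a half-life of about 0.8 h, and AUC0-inf and CL from about 1 h

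*Protocol*

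**What the plan says.** Protocol 7.2.5 has MAD PK samples on Days 1 and 3 "drawn at 15, 30, 45 60, 75, 90, 105, 120, 125, 130, 135, 140 minutes, and 3 hours from the onset" of the infusion. Footnotes 1 and 3 of the MAD timetable and section 7.3.6 give the same times. The infusion is "administered intravenously over 2 hours ± 5 minutes" (protocol 10.1.6). After Day 1 the next draw is "PK blood sample: 24 hours (+/- 30 mins) from the onset of the 1st infusion"; after Day 3 it is "PK blood sample: 72 hours (+/- 30 mins) from the onset of the first LSALT infusion", again about 24 h after that day's dose.

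Two other places differ. Protocol 15.0 samples the MAD cohorts at 0.5 to 24 h after administration on Days 1 and 3. SAP 8.1 samples them from 15 min to 12 h after the infusion ends, with a 24 h sample after Day 1.

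SAP 8.2 derives λz, t1/2, AUC0-inf, %AUCexp, Cl/F, Vz/F, AUC0-12, AUC0-24, AUC0-tau and the accumulation ratios for MAD. Its condition on λz is "At least three concentration points will be used in estimating" it, with no limit on extrapolation. SAP 8.3 sets BLQ values after the first measurable concentration to missing. Protocol 3.8 explains the added cohort: "A third MAD cohort of 5 mg administered intravenously daily for 3 days is being proposed to obtain additional pharmacokinetic data". The only half-life given is from the rat (protocol 3.5): "Terminal elimination half-lives of 0.66" to 1.17 h.

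**The concern.** Of the 13 draws after onset, eight fall within the infusion, four in the 20 min after it and one at 1 h after it. The decline is therefore observed for one hour, followed by a gap until about 22 h after the infusion. Half-life, extrapolated exposure, clearance and volume all depend on that decline. AUC0-12, AUC0-24 and AUC0-tau, and the accumulation ratio built on them, depend on a part of the curve with no samples. At stake is the one purpose stated for the 5 mg MAD cohort, together with the Day 1 to Day 3 comparison and the dose-proportionality slope for AUC0-inf.

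**Working it through.** The plan states no precision or human half-life to reproduce, so the check goes from the sampling times to what they can support.

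**Inputs from the documents.** Infusion 2 h; post-infusion draws at +5, +10, +15, +20 and +60 min; next draw 22 h after the end of infusion; linear trapezoid; late BLQ values missing; rat half-life 0.66-1.17 h.

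**Assumptions not in the documents.** One compartment, 15% residual CV, LLOQ 2% of Cmax, and human half-life unknown and therefore varied.

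**1. The 24 h sample.** It lies 22/1.17 = 18.8 to 22/0.66 = 33.3 half-lives after the infusion, so at rat values it would be BLQ and dropped. It is quantifiable only if t1/2 ≥ 22·ln2 / ln(Cmax/LLOQ): about 5.1, 3.3 or 2.2 h for a Cmax/LLOQ of 20, 100 or 1000, and 15.25/ln 50 = 3.9 h at the assumed 2%.

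**2. Precision of λz.** The five post-infusion times have mean 22 min. Sxx = 17² + 12² + 7² + 2² + 38² = 1,930 min² = 0.536 h², with square root 0.732 h. SE(λz) = 0.15/0.732 = 0.205 per h. Dividing by λz = ln2/t1/2 gives the relative SE below.

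**3. Extrapolated share of AUC0-inf.** With the last sample at 3 h and k = ln2/t1/2, the share is (1 − e^(−2k))·e^(−k)/(2k). At 1.17 h, k = 0.592 and the share is 0.694 × 0.553/1.185 = 32.4%. It reaches 20% at about 0.80 h.

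**4. Simulated non-compartmental analysis, 7.2.5 grid, 24 h sample not quantifiable.**

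| True t1/2 | Relative SE of λz | Extrapolated share | t1/2 within 30% | CL within 20% | 90% range, estimated/true t1/2 |
|---|---|---|---|---|---|
| 0.5 h | 15% | 8.5% | 94% | >99% | – |
| 0.66 h | 20% | 14.6% | 87% | 99% | 0.76-1.46 |
| 1.17 h | 35% | 32.4% | 64% | 78% | 0.64-2.3 |
| 2 h | 59% | 51% | 42% | 42% | 0.5-4.5 |
| 4 h | 118% | 71% | 22% | 17% | – |

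**5. Longer half-lives.** Once the 24 h sample is quantifiable and the decline is mono-exponential, t1/2 is recovered (within 30% in at least 94% of profiles). One linear trapezoid then spans 3 to 24 h and overstates AUC: median CL is about 0.52 of true at a half-life of 3 h, 0.61 at 4 h, 0.75 at 6 h and 0.92 at 12 h.

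**6. Effect of later draws.** Keep the five post-infusion draws and add 4, 6 and 8 h from onset. At 0.66 h only the 4 h value (2^(−2/0.66) = 12% of Cmax) clears the assumed LLOQ; the 6 h value is 1.5%. Sxx then rises to 2.76 h² and the relative SE falls to 0.15/1.66/1.05 = 8.6%. At 2 h all three are quantifiable, Sxx is 33.3 h², and the relative SE is 0.15/5.77/0.347 = 7.5%. The simulated 90% range of t1/2 narrows to about 0.88-1.16 across 0.66-2 h. With the last sample at 8 h the extrapolated share is (1 − e^(−2k))·e^(−6k)/(2k): 9.0% at 2 h and 20% at 3 h.

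**The case against.** **The schedule may not be the one used.** Under SAP 8.1 the extrapolated share is at most 0.05% over the rat range, 5.0% at 3 h and above 20% only beyond about 5.6 h. Protocol 15.0 also samples into the gap. This stands: the point is conditional on 7.2.5 governing.

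**The grid is not useless.** A reader might infer that the added cohort cannot yield usable PK over most plausible half-lives. The documents do not support that. They give no human half-life. At 0.66 h, CL is within 20% in 99% of profiles, and at 1-1.17 h in 87% and 78%, which is imprecise but not unusable. Single-dose cohorts had finished (protocol 3.7) and SAP 2.2 permits interim PK after each cohort, so human data may have prompted the dense sampling near the end of infusion. That is conjecture, but it cannot be excluded.

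**The three-point minimum.** A reader might also infer that λz could rest on 130, 135 and 140 min alone. At rat half-lives the 3 h value is 35-55% of Cmax, so such a fit would have to discard a quantifiable last point. SAP 8.2 also reports the λz limits and the correlation coefficient, so it would be visible.

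**SAD covers the terminal phase.** The SAD timetable samples the same doses to 12, 24 and 72 h after infusion, which helps for single-dose half-life. It cannot supply Day 3 parameters, AUC0-tau or accumulation ratios. Dose proportionality is only exploratory, which limits that consequence.

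**Conclusion.** The point holds conditionally. If the grid in 7.2.5, the timetable footnotes and 7.3.6 governs, MAD t1/2 and Vz are poorly supported for half-lives from about 0.8 h to several hours. AUC0-inf and CL are poorly supported from about 1 h upward, and still biased at several hours even where a quantifiable 24 h sample rescues t1/2. The partial-interval AUCs and RAUC have no observations between 3 and 24 h. At about 0.5 h or less the grid is adequate.

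The 0.80-1.17 h part of the rat range, (1.17 − 0.80)/(1.17 − 0.66), or about 72% of it (using the unrounded crossing point), exceeds 20% extrapolation. Whether humans fall there is unknown. The sample counts and the gap come straight from the documents; the precision figures rest on the assumed one-compartment model, CV and LLOQ.

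**What to change.** 1. Reconcile protocol 7.2.5, MAD timetable footnotes 1 and 3, 7.3.6, protocol 15.0 and SAP 8.1 to one MAD schedule.
2. In doing so, keep 13 post-onset draws on Days 1 and 3, but move three infusion-phase draws (for example 45, 75 and 105 min) to 4, 6 and 8 h from onset. Leave every post-infusion draw in place.
3. In SAP 8.2, pre-state a limit on %AUCexp (for example 20%). Flag profiles above it and exclude their AUC0-inf, CL and Vz from the summaries and the dose-proportionality model.

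The flag accompanies the relocation and does not replace it. On the unchanged grid it would catch about 13% of simulated profiles at 0.66 h, 49% at 0.8 h and 94% at 1.17 h. A rule requiring the λz points to span two estimated half-lives is not advised: it favours profiles whose half-life is underestimated, and it would suppress CL and AUC0-inf where they are adequate.

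**Cost.** Wording in both documents. Blood volume and visits do not change: participants are confined from Day -1 to Day 4 and already have vital signs at 6 and 10 h and an ECG at 8 h after infusion. The price is coarser sampling during the infusion. At very short half-lives little is lost: at 0.25 h the 4 h value is 2^(−8) = 0.4% of Cmax, below the assumed LLOQ, and all the draws that inform λz remain. Beyond a half-life of about 3 h, sampling to 8 h is itself too short, and a later draw would be needed.

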5.0 STUDY DESIGN

This is a double-blind, placebo-controlled, randomized, adaptive design single and multiple ascending dose study to evaluate the safety and pharmacokinetics of LSALT peptide in healthy participants.

To establish a safe starting dose of LSALT peptide, unblinded low dose escalation will first be performed in a small cohort of participants. 0.01 mg of LSALT peptide will be administered intravenously (IV) once. If no adverse effects are observed following 72 hours, subsequent single (n=1) participants will be administered escalating doses of 0.1 mg, 0.3 mg and 0.5mg every 72 hours. If no adverse effects are observed at the 0.5 mg dose, then the study will proceed to the first cohort of 8 participants (6 active treatment, 2 placebo per dose level) who will receive 1.0 mg of LSALT peptide in a double-blinded fashion. Safety, tolerability, pharmacokinetics (PK), and pharmacodynamics (PD) will be assessed before escalating to the next cohort. Dosing will be completed in two sequential cohorts of 8 participants using doses of 2.5 mg and 5.0 mg. The first 2 participants in each blinded cohort will act as sentinels (1 treatment, 1 placebo) who must show no adverse effects before continuing the study under the current design.

Once safety, PK and PD data are completed in the single ascending dose cohort, and the LSALT peptide is determined to be safe and well-tolerated by the Safety Review Committee (SRC), the multiple ascending dose arm of the study will proceed. The multiple ascending dose arm will consist of 2 cohorts of 8 participants receiving 2 independent doses of the LSALT peptide or placebo once or twice daily for 3 consecutive days. The doses for this arm of the study will consist of the 2 highest doses determined by the SRC to be safe in the SAD cohort. The first cohort will receive drug in a double-blinded fashion. Safety, tolerability, PK, and PD will be assessed before escalating to the next cohort. Each cohort will consist of 6 active treatment, 2 placebo per dose

level. The first 2 participants in each cohort will act as sentinels (1 treatment, 1 placebo) who must show no adverse effects before continuing the study under the current design.

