6.3 Enrollment and Randomization

52 participants will be enrolled in the study. 8 participants will be randomly selected to a substitution list to be used in the event of drop-out. Block randomization method will be used for remaining participants with a sample number of 8/group and a 3:1 treatment:placebo ratio. A Randomization Plan will be created, and the randomization of eligible study participants will be managed as per the plan. A Randomization and Substitution List will be prepared using a statistical software package.

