7.1 Single Ascending Dose (SAD) Cohort

7.1.1 Sample Size. The study sample size will be 4 + 24 participants for the SAD arm of the protocol. The first 4 participants will comprise a low dose escalation cohort, and 3 cohorts of 8 (6 treatment and 2 placebo) will comprise the single ascending dose cohorts.

7.1.2 LSALT Peptide Dosing. It is anticipated that seven single intravenous doses of LSALT peptide (0.01 mg, 0.1 mg, 0.3 mg, 0.5 mg, 1 mg, 2.5 mg and 5 mg) will be administered in this arm of the study.

The first 4 participants will each sequentially receive a single escalating low dose of the LSALT peptide (0.01 mg, 0.1 mg, 0.3 mg or 0.5 mg). Escalation to the next dose and participant will occur every 72 hours if no adverse effects are seen. Participants will then be enrolled in cohorts of 8 and randomized to treatment or placebo in a 3:1 ratio. The dose for the first SAD cohort will be 1 mg administered intravenously once over 2 hours. The first 2 subjects of each cohort will be sentinels (1 treatment, 1 placebo). Continuation of the study in each cohort will occur if no clinical or biochemical adverse effects are observed in the sentinels as determined by the Safety Review Committee (SRC). Escalation to the higher dose cohorts (2.5 mg and 5 mg) will occur after 10-14 days if no clinical or biochemical adverse effects are observed in the prior cohort.

A rationale for the proposed doses is based on the NOAEL in dogs (2.5 mg/kg) and the minimum effective dose in mice (0.1-1 μ g/kg). The human equivalent dose is 1.4 mg/kg. The 1 mg dose (16.7 μ g/kg in a 60 kg human) is 1200-fold less than the maximum tolerated dose of 20 mg/kg in dogs, 150-fold lower than the NOAEL and provides a safety factor of 83 relative to the calculated human equivalent dose. The 5 mg dose (83.3 mcg/kg in a 60 kg human) is 240-fold less than the maximum tolerated dose of 20 mg/kg in dogs, 30-fold less than the NOAEL and provides a safety factor of 17 relative to the calculated human equivalent dose. Based on the minimum therapeutic dose observed in mice (0.1 - 1 μ g/kg), a conservative first dose of 0.01 mg (166.7 ng/kg in a 60 kg human) is chosen to further increase the safety margin of the starting dose by 100-fold (i.e. 8400 x less than the human equivalent dose calculated from the NOAEL).

7.1.3 Confinement. Participants will be confined for 24 hours following infusion of the LSALT peptide or placebo.

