3.5. Determination of Sample Size

No prospective calculations of statistical power have been made. The sample sizes of 4 subjects (low dose cohort), 24 subjects for the SAD portion and 24 subjects for the MAD portion of this study have been selected to provide information on safety, tolerability, PK and PD following single and multiple doses of LSALT peptide.

This document is confidential.

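### Protocol 6.3 leaves 44 participants for 52 dosing places, the replacement rules conflict, and the consequences of a withheld multiple-dose infusion are not stated

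*Protocol*

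**What the plan says.** **Numbers.** Protocol 6.3 states "52 participants will be enrolled in the study. 8 participants will be randomly selected to a substitution list" for use at drop-out, and continues "Block randomization method will be used for remaining participants with a sample number of 8/group" in a 3:1 ratio. Protocol 7.1.1 states "The study sample size will be 4 + 24 participants for the SAD arm of the protocol". Protocol 7.2.1 states "The study sample size will be 24 for the MAD arm of the protocol in cohorts of 8". SAP 3.5 counts 4 low-dose participants, then "24 subjects for the SAD portion and 24 subjects for the MAD portion", and SAP 3.6 tabulates three MAD cohorts. Protocol 5.0 still reads "The multiple ascending dose arm will consist of 2 cohorts of 8 participants".

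**Replacement.** Protocol 7.2.4 has people from a reserve pool enrolled and randomized when someone drops out. SAP 3.7 repeats this and then has the replacement receive the treatment of the person replaced, so that the allocation ratio is kept. It also says that a Randomization Plan covers replacements.

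**Blind.** Protocol 6.4 blinds participants and study staff. Protocol 9.9 unblinds staff and the principal investigator for any event of Grade 2 or higher.

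**Repeat doses.** Protocol 7.2.5 says for Day 2 "If the participant shows no adverse events, they will receive the second dose of the LSALT peptide" and for Day 3 "If the participant shows no adverse events, they will receive the third dose of the LSALT peptide". No grade, causality or decision-maker is attached. Protocol 8.0 pauses the study at one event of Grade 3 or higher, or at two Grade 2 events in a cohort.

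**Analysis.** SAP 8.2 derives a Day 3 steady-state AUC0-tau and the accumulation ratios RAUC and RCmax. SAP 5.4 admits anyone given any LSALT who has one estimable parameter.

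**The concern.** A literal reading of 6.3 cannot fill the third MAD cohort, which Protocol 3.8 proposes in order to obtain more PK data. The two replacement instructions cannot both be followed. They also determine whether the 6:2 split survives a replacement and whether staff can work out a replacement's arm.

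The condition in 7.2.5 is what could call these provisions into use. One Grade 1 event, or one Grade 2 event, fails that condition without reaching the pause rule in 8.0. Neither document then says whether the participant has dropped out, may have the next dose, or belongs in the Day 3 PK summaries. This applies to every MAD cohort, not only 5 mg. Because the trigger is an adverse event, the missing or altered Day 3 data may be related to treatment, so the handling should be fixed before unblinding.

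**Working it through.** **1. Places.** Inputs are Protocol 5.0, 6.3, 7.1.1 and 7.2.1, and SAP 3.5.
- The stated total reproduces with no reserve: 4 + 24 + 24 = 52.
- Under 6.3 read literally: 52 − 8 = 44. After the 4 low-dose participants, 40 = 5 × 8 remain. Six cohorts need 6 × 8 = 48.
- Shortfall: 52 − 44 = 8, exactly one cohort.
- The two-cohort text of 5.0 also reproduces 52: 4 + 24 + 16 = 44, and 44 + 8 = 52. This suggests, as an inference, that the total was not raised when the third MAD cohort was added.
- Keeping 52 dosed places and 8 reserves needs 52 + 8 = 60.
- With 44 participants only two MAD dose levels can be filled, and SAP 8.4 requires at least three for the power model.

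**2. Replacement and the 6:2 split.** Assume that any of the 8 in a cohort is equally likely to be replaced and that the replacement is drawn independently at 3:1. The split is kept if an active participant is replaced by an active one, or a placebo participant by a placebo one: 6/8 × 0.75 + 2/8 × 0.25 = 0.5625 + 0.0625 = 0.625. The inherited-arm rule keeps it always. The two rules are therefore different procedures.

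**3. Blind.** The chain is: a Grade 2 or higher event (9.9 unblinds staff), then treatment as a drop-out, then actual replacement, then use of the inherited-arm rule. Staff who know the first participant's arm can then infer the replacement's, contrary to 6.4. If any link is absent, the problem does not arise.

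**4. A withheld dose: what is and is not defined.**
- Defined: Safety Population (SAP 5.2), PK populations (5.3, 5.4), withdrawals kept up to withdrawal with no imputation (6.3), exposure by dose (10.1), follow-up (Protocol 7.3.8).
- Not defined: drop-out status; whether dose 3 may follow a missed dose 2; whether a two-dose profile enters Day 3 AUC0-tau, RAUC and RCmax.

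**5. Size of the PK effect.**
- Planned slope interval (SAP 8.4): 90% half-width = t(0.95, N − 2) × SD / √Sxx, with x = ln(dose) at 1, 2.5 and 5 mg. With 6, 6 and 6 active participants it is 0.624 SD; with 6, 6 and 5 it is 0.654 SD. The ratio is 1.047, about 5% wider.
- At assumed CVs of 30% and 80%, the half-width goes from 0.183 to 0.192 and from 0.439 to 0.460. The criterion is 1 ± ln 2/ln 5, that is ± 0.431.
- Skipped dose 2, one-compartment model, 24 h interval, r = 2^(−24/half-life): the Day 3 to Day 1 ratio is 1 + r + r² with all doses and 1 + r² without dose 2. At the longest rat half-life in Protocol 3.5 (1.17 h), r = 6.7 × 10⁻⁷, so the difference is nil.
- No human half-life is given. At purely assumed values of 6, 12 and 24 h the ratio would be 5.9%, 19.0% and 28.6% too low.

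**The case against.** The strongest reply is that these are drafting slips with little numerical consequence, and that other documents may resolve them. Much of it stands.

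- **The reserve may lie outside the 52.** Protocol 7.2.4 has reserves enrolled only at drop-out, and SAP 3.4 says approximately 52. A reader might infer that the third cohort consumes the 8 substitutes; the documents do not establish that. But 6.3 takes the 8 from the 52, so 6.3 and 7.2.4 disagree.
- **The Randomization Plan may settle the mechanics.** It is not available. It cannot remove opposing instructions from the protocol and SAP.
- **A withheld dose does not leave a participant without any defined status.** The SAP covers most of it, and SAP 5.4 leaves estimability to the pharmacokineticist in consultation with the sponsor. The gap is limited to the three items under step 4.
- **The bar on waivers does not make withholding automatic in every case.** Protocol 9.8 also provides for planned deviations approved by the sponsor and ethics committee.
- **Protocol 9.9 does not itself contradict the replacement rules.** The blinding problem is conditional, and a Grade 1 event never starts it.
- **Larger PK losses are tempting but unsupported.** The interval for a 5 mg Day 3 mean would widen by 16% with five participants instead of six, but the SAP plans no such interval. Accumulation errors of 6% to 29% rest on half-lives found nowhere in the documents.

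**Conclusion.** Two things are wrong as written. First, 6.3 supplies 44 participants for 52 places, short by exactly one cohort. Second, the replacement rule is stated in two incompatible ways; an independent 3:1 draw would keep the 6:2 split only 62.5% of the time, under the assumptions in step 2. Neither finding needs an event rate.

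The blinding exposure is real but conditional on the full chain in step 3. The withheld-dose gap is real but narrow, and it affects all MAD cohorts. Its PK effect is small where calculable: about 5% on an exploratory slope interval for one lost 5 mg participant. For a skipped dose 2 it is negligible at rat half-lives and unknown in humans. The case for correction rests on consistency, allocation and blinding, not on lost precision.

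**What to change.** 1. **Protocol 6.3 and 5.0:** state 52 dosing places with the 8 reserves outside that number (up to 60 in total, reserves dosed only if needed), or state that no reserve remains. Align 5.0 with three MAD cohorts.
2. **Protocol 7.2.4 and SAP 3.7:** keep one replacement-assignment rule in both, applied by unblinded staff. In the safety listings, identify any replacement whose arm could be inferred from an unblinding under 9.9.
3. **Protocol 7.2.5 with 7.2.4, 8.0 and 9.8:** reconcile these on what follows a withheld dose, who decides, and whether it counts as drop-out. The clinical rule is for the sponsor and the Safety Review Committee.
4. **SAP 5.4 and 8.2:** flag and list participants not given all three infusions, and present Day 3 AUC0-tau, RAUC and RCmax with and without them. This avoids discarding profiles that a missed dose may not have altered.

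The cost is wording changes, a small amount of extra analysis and, if the reserve is kept, a higher stated enrolment ceiling. No new study procedures are needed.
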